8.4.2 Serious Adverse Event Reporting

SAEs are not expected due to participation in this minimal risk study. The procedure for AE reporting will be followed for SAEs. In addition, if a serious adverse event occurs, it will be reported in a timely fashion after adjudication: All SAE reports will be made to the IRB within 5 working days; any participant deaths will be reported to the NINR Program Officer within 24 hours of realization, and all other serious adverse events will be reported to NINR within 72 hours of realization.

CONFIDENTIAL

This material is the property of the NYU School of Medicine and NYU Langone Health. Do not disclose or use except as authorized in writing by the study sponsor
Behavioral Intervention Template Version: 11 January 2019

8.4.3 Unanticipated Problem Reporting

Incidents or events that meet the OHRP criteria for UPs require the creation and completion of an UP report form. It is the site investigator's responsibility to report UPs to their IRB and to the DCC/study sponsor. The UP report will include the following information:

- Protocol identifying information: protocol title and number, PI's name, and the IRB project number;
- A detailed description of the event, incident, experience, or outcome;
- An explanation of the basis for determining that the event, incident, experience, or outcome represents an UP;
- A description of any changes to the protocol or other corrective actions that have been taken or are proposed in response to the UP.

To satisfy the requirement for prompt reporting, UPs will be reported using the following timeline:

- UPs that are SAEs will be reported to the IRB and to the study sponsor within the timeframe described in 8.4.2 of the investigator becoming aware of the event.
- Any other UP will be reported to the IRB and to the study sponsor within the timeframe described in 8.4.1 for AEs of the investigator becoming aware of the problem.
- All UPs should be reported to appropriate institutional officials (as required by an institution's written reporting procedures), the supporting agency head (or designee), and OHRP within the time frame described for AEs or SAEs, as appropriate, of the IR's receipt of the report of the problem from the investigator.

8.4.4 Reporting of Pregnancy

Pregnant or breastfeeding participants will not be able to participate in the study because pregnancy and lactation can disrupt habitual sleep patterns, and hormonal changes during pregnancy increase insulin resistance⁹³. Female participants of child bearing potential will be asked to use a medically accepted method of birth control while in the study. If participants become pregnant during the course of the study, their data will not be used in the analyses.

8.6 Reporting Procedures – Participating Investigators

Not applicable.

CONFIDENTIAL

This material is the property of the NYU School of Medicine and NYU Langone Health. Do not disclose or use except as authorized in writing by the study sponsor
Behavioral Intervention Template Version: 11 January 2019

8.7 Study Halting Rules

As this study is minimal risk, it is not anticipated that the study may be halted. However, if there is a determination of unexpected, significant, or unacceptable risk to participants, the study may be temporarily suspended or prematurely terminated as described in section 6.7

8.8 Safety Oversight

It is the responsibility of the Principal Investigator to oversee the safety of the study at his/her site. This safety monitoring will include careful assessment and appropriate reporting of adverse events as noted above, as well as the construction and implementation of a site data and safety-monitoring plan. [name], CRNP, will be the medical monitor of the study and will review participant safety data including adverse event on a monthly basis as described in this section. [name] is a certified registered nurse practitioner (CRNP) and is qualified to oversee the safety of participants in this study. It is within the scope of practice for nurse practitioners to care for patients throughout their lifespan. This may include the diagnosis of illness and physical conditions and the performance of therapeutic and corrective measures.

Medical monitoring will include a regular assessment of the number and type of serious adverse events.

The following are plans for data and safety monitoring during this R00 study:

Monitoring entity. This study will be monitored by the PI, the project coordinator, the bio-statistician, and the IRB. The PI will ensure that the project coordinator undergoes training in the study protocol. The project coordinator will be trained in the safety protocol for depression. The PI will oversee adherence to the study protocol to ensure the safety, reliability, and validity of data collection. The PI will be responsible for submitting all necessary reports to the study sponsor and the IRB. The project coordinator will prepare monthly reports on participant demographics, recruitment, attrition, data collection, data entry updates, and any other issues or concerns since the last research team meeting. These reports will also contain a summary of monthly accrual and cumulative accrual, a summary of key characteristics of the study participants, and a summary of the completeness and quality of data. The statistician will prepare reports about missing, invalid, or inconsistent data on selected key variables as needed.

Monitoring Study Safety. Once enrollment is initiated, the PI will arrange monthly meetings with the project coordinator and research assistant. These meetings will consist of retrospective and concurrent evaluation of all research procedures, including participant screening for inclusion/exclusion criteria, the informed consent process, and participant study instructions, as well as any necessary staff training in the IRB approved study protocol. The PI and Co-I will meet quarterly to review the study progress. Meetings will also be arranged by the PI if an adverse event occurs.

Minimizing research-associated risk. We do not believe that there are any major risks associated with the proposed study, although a subject may be identified with OSA risk, T2DM, or moderate/severe or severe depression. This is not a research-associated risks but may be detected during screening or participation in the study. The sleep intervention and accelerometry monitoring have minimal risk. Trained research personnel will perform all testing and will be monitored by the PI. Throughout the study, the PI and the research coordinator will monitor participants for adverse events and for adherence to the study protocols. We have developed the following medical alert and reporting policies:

1. ARES questionnaire ≥ 6
 - a. For participants not eligible for the at-home assessment, refer the participant to a nearby sleep disorders center for further evaluation.
 - b. For participants that are eligible for the at-home assessment, complete 1 night of at-home pulse oximetry.
2. Pulse oximetry AHI > 10
 - a. Refer diagnosed and treated OSA participants to their health care provider.

CONFIDENTIAL

- b. For undiagnosed OSA participants, refer the participant to a nearby sleep disorders center for further evaluation.
3. PHQ-9 response to question 9
 - a. Participants responding “several days”, “more than half the days” or “nearly every day” to the PHQ-9 question: “Over the past 2 weeks, how often have you been bothered by any of the following problems?....Thoughts that you would be better off dead or of hurting yourself” will be screened further at the CTSI visit 1 by the project coordinator as per the Depression Safety and Referral Protocol.
 - b. See the Depression Safety and Referral Protocol.
4. HbA1c point of care fingerstick results $\geq 6.5\%$
 - a. Participants will be notified of HbA1c point of care fingerstick results $\geq 6.5\%$ at the CTSI visit.
 - b. Participants will be instructed to share the results with their PCP. If the participant does not identify a PCP, the authorized prescribing provider ([name]) is notified and a referral made to the NYU Faculty practice health care providers.

Protecting Participant Confidentiality.

Participant Screening and Enrollment. When individuals are contacted to determine their interest in participating in the study, no language will be used that will indicate any study opportunity/eligibility or personal health information unless research personnel are speaking directly with the party of interest. All data from participants screened for the study will be entered into the Research Electronic Data Capture (REDCap). The collected data will be helpful in examining the patient population and feasibility of enrollment criteria and will include gender, age, race, and reason for exclusion. For retained participants, the research staff will collect and enter required data (written informed consent and demographics) onto study data forms in REDCap. Individuals will be assigned a unique study ID number.

Only the PI and the study team will have access to the linkage between the participant identity and the study identification number. This linkage will be password protected and stored on a secure NYU server.. This linking file will be destroyed at closure of the study, and the study will remain open with the IRB until these identifiers are destroyed. The unique study identification number will be used on all data forms. Paper records, such as the informed consent documents, will be kept in a locked file cabinet in a locked office. All data will be reported in aggregate.

Binders. A regulatory file will also be maintained to include the IRB- approved protocol, original informed consent documents, and other study-related regulatory documents. All paper research records and case record files will be maintained in a locked file cabinet in a secure facility within the College of Nursing. Access to the research records, study database and PHI's will be restricted to study personnel as approved by the PI and IRB.

Data entry, processing, monitoring. This study will use REDCap for data capture and management. Data exports will be limited to the PI, the project coordinator, and the statistician for generating reports and conducting statistical data analysis. Monthly meetings will include reports on participant recruitment and retention, adverse events, and protocol deviations, as well as summaries of monthly accrual and cumulative accrual, key characteristics of the study participants, and the completeness and quality of data. Information on missing, invalid, and inconsistent data on selected key variables will be reviewed.

Data Security. All data will be saved in an electronic database on a secure NYU server. All system logins, data entries, and data updates are recorded, enabling efficient data tracking. Access to the server is available only to authorized users with passwords; overall data security is ensured by a firewall.

Additional security is provided by database software requiring a password for data entry and allowing for password protection at the record level within a database. Patient confidentiality will be ensured by eliminating from the design of the data systems any information that could be used to identify individual participants. Each participant will be identified in the database by a project-specific ID number. Identifiable

CONFIDENTIAL

information (e.g., name, birthdate, home address, or other personal information) will not be stored on any of the devices used in this study. For mobile devices and software such as the tablets or cell phones that will be used to gather survey data, guidelines established by NYU IRB will be followed including documentation of security controls, incident response program, compliance certifications, privacy practices, physical data security, and subcontractors. The packages that are shipped to and from study participants will not have any information on the exterior of the box indicating that they are a research participant.

External factors. The PI will monitor developments in the literature as the study progresses. Should it become clear that the intervention would be in any way harmful to participants, would increase risk, or would be unethical to continue, the IRB and study sponsor will be notified and the study will be stopped.

Futility analysis. As this randomized clinical trial will also be used to provide preliminary data (e.g., effect sizes) for a future well-powered R01 application, we will not do a futility analysis.

9 Clinical Monitoring

Clinical site monitoring is conducted to ensure that the rights and well-being of human subjects are protected, that the reported trial data are accurate, complete, and verifiable, and that the conduct of the trial is in compliance with the currently approved protocol/amendment(s), with GCP, and with applicable regulatory requirement(s).

- The PI or project coordinator will audit one case per quarter, selected at random, to confirm compliance with IRB requirements, including conformance with informed consent requirements, verification of source documents, and investigator compliance.
- Authorized representatives of the IRB and the NINR may review de-identified information, as well as participants' identifiable information, for the purposes of assuring proper conduct of the research, addressing a specific reported incident, or verifying appropriate use of funds. The Quality Assurance and Quality Improvement Division of NYU's Research and Regulatory Services may audit the study to confirm compliance. Access of any protected health information will be done in the offices of the PI in his presence. No identifiable information may be copied or taken off-site.

10 Statistical Considerations

10.1 Statistical and Analytical Plans

A formal SAP will be developed for this study in consultation with the study biostatistician. Only a general overview of study statistics is included in this protocol.

10.2 Statistical Hypotheses

Sleep intervention participants will have a lower percentage of time glucose is $\geq 140\text{mg/dL}$ compared to control intervention participants after 8-weeks of treatment.

10.3 Analysis Datasets

Primary analyses will be performed within an intent-to-treat (ITT) sample, including all participants that are randomized to either the Sleep Intervention or Control Intervention.

10.4 Description of Statistical Methods

10.4.1 General Approach

The goal of this single site, parallel arm randomized clinical trial is to assess the impact of improved sleep on glycemic control (percent time glucose is ≥ 140) when compared to habitual sleep. Using descriptive

CONFIDENTIAL

This material is the property of the NYU School of Medicine and NYU Langone Health. Do not disclose or use except as authorized in writing by the study sponsor
Behavioral Intervention Template Version: 11 January 2019

analyses, the investigators will describe each variable using measures of central tendency (means, medians) and variability (standard deviations, interquartile ranges) for continuous variables; counts and percentages for categorical variables. Data will be evaluated for anomalies (e.g., nonrandom missing data, erroneous outliers, multicollinearity, possible confounding) that may invalidate planned analyses. Data transformations, imputation, and/or robust and tailored analysis approaches will be used for non-normally distributed variables.

10.4.2 Analysis of the Primary Efficacy Endpoint(s)

Linear regression models will be used to assess the effect of the sleep intervention with the subject specific change in the percent time glucose is ≥ 140 from baseline as the continuous outcome variable and intervention arm (0=Control Intervention, 1=Sleep Intervention) as a dichotomous predictor. Effect sizes will be presented as beta coefficients and associated 95% confidence intervals, equal to the expected difference between the SI and CI. Important covariates that will be controlled for in these analyses include demographic characteristics including age, sex, race/ethnicity and behaviors characteristics including diet quality and physical activity. The rationale for including these covariates is because of their associations with both sleep and glycemic control. Statistical significance will be determined with a p -value < 0.05 using a two-tailed test for significance.

10.4.3 Analysis of the Secondary Endpoint(s)

The same analytic approach described in Section 10.4.2 will be used to assess the effect of the sleep intervention with the subject specific change in glucose variability.

10.4.4 Safety Analyses

As this study is minimal risk, it is not anticipated that the study may be halted. However, if there is a determination of unexpected, significant, or unacceptable risk to participants, the study may be temporarily suspended or prematurely terminated.

10.4.5 Adherence and Retention Analyses

Intervention compliance will be defined by 80% completion rate of daily sleep diaries and 80% attendance at the intervention sessions.

10.4.6 Baseline Descriptive Statistics

Demographic and other measures will be compared between the sleep intervention and control intervention arms at baseline using T-tests or Wilcoxon rank sum tests for continuous measures and chi-squared or Fisher's exact tests for categorical variables. Given the randomized nature of the study design, the two arms are expected to be balanced with respect to all baseline characteristics; in the unlikely case that there is imbalance in important covariates, these measures will be adjusted for in statistical models.

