Description of Study Intervention/Procedure	The sleep intervention arm will receive a personalized sleep intervention that is based on Cognitive Behavioral Therapy for Insomnia (CBT-I). Like CBT-I, the sleep intervention extends sleep based on sleep efficiency. Bedtimes and wake times will be prescribed each week for each participant and allow for gradual adjustments in sleep opportunity. Bedtimes will be set 15 minutes earlier each week provided sleep efficiency remains greater than 90%. Earlier bedtimes will extend sleep duration by increasing the opportunity for sleep. 2019 American Diabetes Association (ADA) Standards of Medical Care recommendations for physical activity and nutrition in adults with prediabetes will also be included.
Reference Therapy	The control arm will receive lifestyle intervention recommendations according to ADA Standard of Medical Care for physical activity and nutrition. Generic sleep recommendations will also be included.

CONFIDENTIAL

This material is the property of the NYU School of Medicine and Langone Health. Do not disclose or use except as authorized in writing by the study sponsor

Key Procedures	
Baseline and end-of-treatment surveys Daily sleep diaries Weekly sleepiness surveys 14 days of continuous wrist accelerometer wear time at baseline and end-of-treatment 7 days of continuous glucose monitoring wear time at baseline and end-of-treatment

Statistical Analysis	
Linear regression models will be used to assess the effect of the sleep intervention versus the control intervention on the percent time glucose is greater than or equal to 140 mg/dL. The outcome variable will be the percent time glucose is greater than or equal to 140 mg/dL. The dichotomous predictor variable will be the intervention arm (0 = control, 1 = sleep intervention).

CONFIDENTIAL

This material is the property of the NYU School of Medicine and NYU Langone Health. Do not disclose or use except as authorized in writing by the study sponsor
Behavioral Intervention Template Version: 11 January 2019

Schematic of Study Design

Visit 1/Day 0 CTSI visit 1 Screening

- Total n= 800 to retain 400 for at home screening
- Obtain informed consent
- Screen potential subjects by inclusion and exclusion criteria
- Complete the following screening surveys (AUDIT, ARES, Insomnia Severity Index, selected questions from the Sleep Disorder Symptom Checklist (SDS-CL 25), PHQ-9, NINR Demographics)

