- Obtain targeted health and medication history and brief physical (height, weight, waist, neck circumference, blood pressure, Hemoglobin A1c point of care test, optional blood draw)

Weeks 1-2/Days 1 - 14 At-home screening and baseline assessments

- Total n= 400 to retain 188 for intervention
- Wrist accelerometer (24/7 for 14 nights); Continuous glucose monitor (CGM) (24/7 for 7 days); Pulse oximeter (for 1 night, as needed); Sleep Diaries (daily); Social Rhythms Metrics (SRM-5), Epworth Sleepiness Scale (weekly); ASA24 hour dietary recall; Composite Scale of Morningness; International Physical Activity Questionnaire; Pittsburgh Sleep Quality Index; PROMIS-Depression 6a; Sleep Environment Survey

Week 3/Days 15 - 21 Randomization

- Sleep intervention group (n=94 enrolled to retain n=75)
- Attention control group (n=94 enrolled to retain n=75)

Weeks 4-11/Days 22 - 77 Study Intervention

- Administer study intervention (weekly)
- Sleep Diaries (daily); Epworth Sleepiness Scale (weekly)

Visit 2/Days 78-84 CTSI visit 2.

- ASA24 hour dietary recall; International Physical Activity Questionnaire; Pittsburgh Sleep Quality Index; PROMIS-Depression 6a
- Weight, waist, and blood pressure measurements

Weeks 12-13/Days 78 - 91 End of Study Assessments

- Wrist accelerometer to be worn 24/7 for 14 nights. Continuous glucose monitor (CGM) to be worn 24/7 for 7 days.
- Sleep Diaries (daily); Social Rhythms Metrics (SRM-5), Epworth Sleepiness Scale (weekly)
- Final visit (optional)

CONFIDENTIAL

This material is the property of the NYU School of Medicine and NYU Langone Health. Do not disclose or use except as authorized in writing by the study sponsor
Behavioral Intervention Template Version: 11 January 2019

1 Key Roles

*[name] [name], Assistant Professor
NYU Rory Meyers College of Nursing
[name]
[contact]
[contact]*

*[name], EdD Professor with Chair, Academic Vice Dean
NYU Rory Meyers College of Nursing
[name]
[contact]
[contact]*

*[name]
NYU Langone Health, Ronald O. Perleman Department of Emergency Medicine
[name]
[contact]
[contact]*

*[name] [name], CRNP, Associate Professor, Academic Director
NYU Rory Meyers College of Nursing
[name]
[contact]
[contact]*

*Clinical and Translational Science Institute, Bellevue Hospital
[name]
[name]
[contact]
[contact]*

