### **1.3.2 Analysis of the Primary Efficacy Endpoint(s)**

A multivariable Linear regression model was used to assess the effect of the sleep intervention with the subject specific change in the percent time glucose is  $\geq 140$  (Time above target) from baseline as the continuous outcome variable and intervention arm (0=Control Intervention [CI], 1=Sleep Intervention [SI]) as a dichotomous predictor. Effect sizes were presented as beta coefficients and associated 95% confidence intervals, equal to the expected difference between the SI and CI. Important covariates that will be controlled for in these analyses include demographic characteristics including age (continuous), sex (female/male), and race (Asian, Black, White, Other). Statistical significance was determined with a  $p$ -value  $< 0.05$  using a two-tailed test for significance. Normality was assessed using a skewness cutoff of  $\pm 2$ , following established guidelines.

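### Protocol 10.4.6 tests randomised baseline measures and lets an undefined imbalance judgement add covariates; replace it with one prespecified covariate set shared with the SAP

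*Protocol*

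**What the plan says.** Protocol 10.4.6 (Baseline Descriptive Statistics) states: "Demographic and other measures will be compared between the sleep intervention and control intervention arms at baseline using T-tests or Wilcoxon rank sum tests", with chi-squared or Fisher tests for categorical variables. It expects balance on every baseline characteristic because the trial is randomised, and adds that, "in the unlikely case that there is imbalance in important covariates, these measures will be adjusted for in statistical models". The section gives no significance level for these tests, no other measure of imbalance, and no list of the covariates that count as important.

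The covariates for the outcome model are stated elsewhere, in two versions:

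- Protocol 10.4.2: "demographic characteristics including age, sex, race/ethnicity and behaviors characteristics including diet quality and physical activity".
- SAP 1.3.2: "demographic characteristics including age (continuous), sex (female/male), and race (Asian, Black, White, Other". Diet quality and physical activity are absent.

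The outcome in both is the change in percent time at or above 140 mg/dL from baseline. Neither list contains the baseline value of that measure. Protocol 10.4.3 and 10.4.11 apply the 10.4.2 approach to the secondary and exploratory endpoints. Protocol 10.6.1 says that the biostatistician is not blinded to group assignment. The SAP text neither repeats nor withdraws the adjust-if-imbalanced rule.

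**The concern.** When randomisation is sound, every true baseline difference between arms is zero, so a small p-value at baseline reports a chance event. A rule that adds covariates on that basis selects them by how they happened to fall. What makes a covariate useful in the model is how well it predicts glucose change.

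Two things are at stake. First, the final model is not fully fixed in advance. Someone must decide which differences are imbalances and which variables are important, with the data in hand and, under 10.6.1, with knowledge of the arms. Second, a reader holding both documents cannot tell which model is primary: five covariates, three covariates, or either list plus whatever 10.4.6 adds.

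**Working it through.** **Design inputs.** Section 10.4.6 gives no figure behind its word unlikely, so there is none to reproduce there. The sample-size figures in 10.5 do reproduce. A two-sample t-test with a two-sided 0.05 level, 0.6 SD and 95% power needs 73.2, so 74 per arm. Allowing for 20% loss, 150 / (1 − 0.2) = 187.5, so 188.

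**Count of baseline measures.** This is my own count from the Schematic of Study Design and Protocol 4.2:

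- Demographics: age, sex, race (3).
- From "height, weight, waist, neck circumference, blood pressure, Hemoglobin A1c point of care test, optional blood draw": six measures, leaving out the blood draw.
- Screening surveys: AUDIT, ARES, Insomnia Severity Index, PHQ-9 (4).
- At-home surveys: Composite Scale of Morningness, IPAQ, PSQI, PROMIS-Depression, Sleep Environment (5), plus Epworth and SRM-5 (2).
- Devices: actigraphy sleep duration, percent time at or above 140, glucose variability (3).
- Diet: percent carbohydrate, percent fat (2).

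Total: 3 + 6 + 4 + 5 + 2 + 3 + 2 = 25. Sleep-disorder checklist items, income, education and other actigraphy measures are left out and would raise it.

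**Chance of at least one flag.** Assume each baseline test uses 0.05. The documents give that level only for the outcome test. For k independent tests the chance is 1 − 0.95^k.

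| Measures counted | k | Chance of a flag |
|---|---|---|
| Diet quality and activity (in the protocol list, not in the SAP) | 2 | 9.75% |
| SAP list | 3 | 14.3% |
| Protocol 10.4.2 list, diet counted once | 5 | 22.6% |
| Last k below one half | 13 | 48.7% |
| First k above one half | 14 | 51.2% |
| All counted | 25 | 72.3% |

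The measures are not independent. With correlation of 0.3 to 0.8 inside related groups only (for example weight, waist and neck), the figure for 25 falls from about 72% to 66%. If all measures shared one common correlation, 24 of them would give 65% at 0.2, 60% at 0.3 and 46% at 0.5.

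The threshold matters as well. If imbalance meant a standardised difference above 0.25 with 94 per arm, the chance per measure would be 2(1 − Φ(0.25/√(2/94))) = 8.7%. That gives 36% for five measures and 90% for 25.

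**Effect on the outcome test.** The rule can only add terms to a fixed list, so it was simulated that way: 75 per arm, 20 independent covariates, five fixed, and the other 15 added when their baseline p-value is below 0.05. Predictive strength is assumed: three covariates correlated 0.3 with the outcome, three at 0.4, or one at 0.5. Power at a true 0.4 SD, in that order:

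| Where the predictors lie | Fixed list only | Fixed list plus triggered terms |
|---|---|---|
| Inside the fixed list | 80.9 / 91.0 / 79.5% | 79.3 / 90.2 / 78.9% |
| Outside the fixed list | 66.5 / 66.7 / 68.3% | 66.3 / 67.7 / 67.9% |

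The largest loss is 80.9 − 79.3 = 1.6 points. In one setting the trigger gains 1.0 point. At the planning effect of 0.6 SD the difference is at most 0.9 points. With three fixed covariates, as in the SAP, the largest change is about 1.5 points. Type I error across these runs is 3.8 to 5.6%. With three fixed covariates, the triggered terms change the significance verdict in about 1 to 8% of trials, at true effects of 0 and 0.4 SD.

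**The case against.** The strongest reply is that little is left to chance. The outcome, the arm term and three to five covariates are fixed. Section 10.4.6 restricts adjustment to important covariates, and 10.4.2 uses the same term for its five named variables. On that reading the rule adds nothing to the protocol model. Protocol 10.1 calls the section a general overview and defers to the SAP, whose text contains no baseline tests and no trigger. Baseline p-values in a descriptive table are a common convention.

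Much of this stands, and it rules out three stronger readings:

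- **That the outcome model is chosen by chance.** It is not. Only terms beyond the fixed list could vary.
- **That the rule inflates false positives.** The simulated type I error stays close to 5%.
- **That the rule costs 10 to 24 points of power.** One could reach this by comparing the trigger used alone (67 to 70% at 0.4 SD) with fixed adjustment for predictive covariates (80 to 91%). The plan does not pose that choice. The second table shows that the gap comes from whether predictive covariates are in the fixed list at all. Deleting the trigger would not recover it.

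The narrow reading does not dispose of the point. If important covariates means the five in 10.4.2, the sentence has no work to do in the protocol. Under the SAP's three it could still bring in diet quality or activity (9.75% by the first table). If it means more, the set is open. The SAP's silence does not withdraw a rule that the protocol states.

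**Conclusion.** The point holds as a defect of prespecification and is worth correcting, though its numerical effect is modest. Section 10.4.6 states an active rule with no list, threshold or definition, to be applied by an analyst who knows the arms, and it does not match the fixed list in SAP 1.3.2.

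The expectation of balance on every baseline characteristic is not supported. With about 25 measures tested at an assumed 0.05, a flag is more likely than not (66 to 72%) unless the measures share a strong common correlation. A reader might infer that the model itself is therefore more likely than not to change. The documents do not support that, because a flag matters only if the variable is also judged important and is not already in the model. For the five named covariates the chance is 23% and the protocol model stays the same.

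These sizes rest on the assumed 0.05 trigger, my count of measures, and simulated independent covariates with assumed predictive strength.

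**What to change.** 1. In Protocol 10.4.6, delete the significance tests and the sentence that adjusts for imbalanced covariates. Report baseline by arm with means and SDs, medians and interquartile ranges, and counts, with standardised differences if wanted.
2. State one identical covariate set in Protocol 10.4.2 and SAP 1.3.2, chosen as expected predictors of the outcome and not altered by observed imbalance. Include the baseline value of percent time at or above 140 mg/dL. It is already collected and is an arithmetic part of the change score, yet under the present text it could enter only through the 10.4.6 trigger.
3. Label any model with further covariates as a sensitivity analysis.

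The cost is two sentences in 10.4.6 and a matching covariate sentence in each document, with no new data. The downside is that a chance imbalance in some other variable is handled only in the sensitivity analysis.
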